11.6.2 Significance Level and Confidence Coefficient

A two-sided 5% significance level will be used, and a two-sided 95% confidence coefficient will be used for interval estimation.

11.6.3 Missing Data

Missing data will not be imputed and will be excluded from the analysis.

12 ETHICAL CONSIDERATION

12.1 Good Clinical Practice Compliance

This study will be conducted in accordance with the protocol and with the following:

- Consensus ethical principles derived from international guidelines including the Declaration of Helsinki and Council for International Organizations of Medical Sciences International Ethical Guidelines
- Applicable International Council for Harmonization (ICH) Good Clinical Practice (GCP) Guidelines
- Applicable laws and regulations

12.2 Institutional Review Board Approval

The protocol, protocol amendments, ICF, Investigator Brochure, and other relevant documents (eg, advertisements) must be submitted to an IRB by the Investigator and reviewed and approved by the IRB before the study is initiated.

Any amendments to the protocol will require IRB approval before implementation of changes made to the study design, except for changes necessary to eliminate an immediate hazard to subjects.

The Investigator will be responsible for the following:

- Providing written summaries of the status of the study to the IRB annually or more frequently in accordance with the requirements, policies, and procedures established by the IRB
- Notifying the IRB of SAEs or other significant safety findings as required by IRB procedures
- Providing oversight of the conduct of the study at the site and adherence to requirements of Title 21 of the Code of Federal Regulations (CFR), ICH guidelines, the IRB, European regulation 536/2014 for clinical studies (if applicable), and all other applicable local regulations

12.3 Informed Consent

The Investigator or his/her representative will explain the nature of the study to the subjects and answer all questions regarding the study.

Subjects must be informed that their participation is voluntary. Subjects will be required to sign a statement of informed consent that meets the requirements of 21 CFR 50, local regulations, ICH guidelines, Health Insurance Portability and Accountability Act requirements, where applicable, and the IRB or study center.

The medical record must include a statement that written informed consent was obtained and the date the written consent was obtained. The authorized person obtaining the informed consent must also sign the ICF.

Subjects must be reconsented to the most current version of the ICF(s) during their participation in the study.

A copy of the ICF(s) must be provided to the subjects.

12.4 Data Protection

Participants will be assigned a unique identifier by the Sponsor. Any participant records or datasets that are transferred to the Sponsor will contain the identifier only; participant names or any information which would make the participant identifiable will not be transferred.

The participant must be informed that his/her personal study-related data will be used by the Sponsor in accordance with local data protection law. The level of disclosure must also be explained to the participant.

The participant must be informed that his/her medical records may be examined by Clinical Quality Assurance auditors or other authorized personnel appointed by the Sponsor, by appropriate IRB members, and by inspectors from regulatory authorities.

12.5 Financial Disclosure

Investigators and sub-investigators will provide the Sponsor with sufficient, accurate financial information as requested to allow the Sponsor to submit complete and accurate financial certification or disclosure statements to the appropriate regulatory authorities. Investigators are responsible for providing information on financial interests during the course of the study and for 1 year after completion of the study.

13 PROCEDURE FOR COMPLETION AND CORRECTION OF THE CASE REPORT FORM

The procedures for completion of the eCRFs and reconciliation of data queries will be provided in the CRF Completion Guidelines .

14 DIRECT ACCESS TO SOURCE DATA

Source documents provide evidence for the existence of the participant and substantiate the integrity of the data collected. Source documents are filed at the Investigator's site.

Data reported on the CRF or entered in the eCRF that are transcribed from source documents must be consistent with the source documents or the discrepancies must be explained. The Investigator may need to request previous medical records or transfer records, depending on the study. Also, current medical records must be available.

15 DATA QUALITY ASSURANCE

All participant data relating to the study will be recorded on printed or eCRF unless transmitted to the Sponsor or designee electronically (eg, laboratory data). The Investigator is responsible for verifying that data entries are accurate and correct by physically or electronically signing the eCRF.

The Investigator must maintain accurate documentation (source data) that supports the information entered in the eCRF.

The Investigator must permit study-related monitoring, audits, IRB review, and regulatory agency inspections and provide direct access to source data documents.

The Sponsor or designee is responsible for the data management of this study including quality checking of the data.

Study monitors will perform ongoing source data verification to confirm that data entered into the eCRF by authorized site personnel are accurate, complete, and verifiable from source documents; that the safety and rights of participants are being protected; and that the study is being conducted in accordance with the currently approved protocol and any other study agreements, ICH-GCP, and all applicable regulatory requirements.

16 ARCHIVING OF SOURCE DATA AND OTHER RECORDS

Records and documents, including signed ICFs, pertaining to the conduct of this study must be retained by the Investigator for at least 2 years after the last marketing application approval or, if not approved, 2 years following the discontinuation of the test article for investigation. If this requirement differs from any local regulations, the local regulations will take precedence unless the local retention policy is less than 2 years. No records may be destroyed during the retention period without the written approval of the Sponsor. No records may be transferred to another location or party without written notification to the Sponsor.

17 PUBLICATION POLICY

The results of this study may be published or presented at scientific meetings by the Sponsor. The results of and data from this study belong to the Sponsor. No individual subject will be identified in any publication.

The Sponsor will comply with the requirements for publication of study results.

18 COVID-19 PANDEMIC AND SUGGESTED MEASURES

This section is provided in response to the “FDA Guidance on Conduct of Clinical Trials of Medical Products during COVID-19 Pandemic” issued by the FDA on March 2020. Taking the COVID-19 impact into account, this section provides guidance to Investigators and their site staff to mitigate risks and suggested measures to modify operations. Each Investigator may choose to implement different measures according to their sites’ operations; which may include, but are not limited to the following items.

18.1 Screening Questions to Identify Potential COVID-19 Exposure

When scheduling an on-site visit for subjects, consider asking the subjects a few, short questions regarding potential exposure to COVID-19 before their on-site visit (in-person interactions). For example:

1. Have you had any of the following symptoms in the past 14 days without confirmation of etiology such as a positive flu test, existing chronic medical condition, etc.
 - Fever greater than 100.4 degrees Fahrenheit
 - Cough
 - Difficulty breathing
 - Sore throat
2. In the last 14 days, have you lived with, visited, cared for, or been in a room for a prolonged period of time with someone who is under investigation or has been confirmed for COVID-19?

18.2 Screening Window

If a subject has completed all Screening Visit procedures and is eligible to proceed to Study Day 1 but cannot do so within the allotted timeframe of 28 days, it will be considered to extend the visit window on a case by case basis. The BPIC/SS questionnaire must be repeated to ensure it is valid and within 28 days of dosing, but further consultation is necessary with Contract Research Organization (CRO) and may necessitate approval by the study’s Medical Monitor and Sponsor.

18.3 Follow-Up Visit by Phone

Should a subject not be able to complete a study visit in-person, the following procedures will be completed via phone, as necessary by the schedule of events according to the protocol:

1. Medical history
2. IC/BPS history and treatment history
3. Concomitant medication and therapy information
4. Adverse events
5. PRO questionnaires (BPIC-SS, ICSI/PI and GRA)

Site staff will capture the above in the source documents and promptly notify CRO and Clinical Research Associate (CRA) of the partial phone visit as soon as possible. All missing data, and the phone visit itself, will be considered protocol deviations. Site staff will need to complete additional forms for IRB submission and state "COVID-19" in the comment column of the deviation log.

18.4 Remote Monitoring

Due to travel restrictions, shelter in place or stay at home mandates, sites' change in operations, and a number of other reasons to try to contain the spread of the virus and minimize exposure, it is reasonable to conduct monitoring visits remotely, instead of in-person, whenever feasible. Site staff/Investigator will work with CRO and the assigned CRA to define and understand the logistics of the remote visit such as source data verification.

18.5 Data Management

In order to confirm the effect of COVID-19 on this study, the following information will be captured in eCRF.

- Missed visit due to COVID-19
- Missed assessment due to COVID-19
- Screen failed subject due to COVID-19
- Early discontinuation due to COVID-19
- AE related to COVID-19

Appendix 1 Clinical Laboratory Tests

- The tests detailed in [Table 4](#) will be performed by central clinical laboratories.
- Protocol-specific requirements for inclusion or exclusion of subjects are detailed in [Section 4.1](#) and [Section 4.2](#) of the protocol.
- Additional tests may be performed at any time during the study as determined necessary by the Investigator or required by local regulations.

Table 4 Protocol-required Safety Laboratory Assessments

Laboratory Assessments	Parameters	
Hematology	Platelet count Red blood cell (RBC) count Hemoglobin Hematocrit	White blood cell (WBC) count with differential: Neutrophils Lymphocytes Monocytes Eosinophils Basophils
Coagulation	partial thromboplastin time (PTT) prothrombin time/international normalized ration (PT/INR)	
Clinical chemistry	Blood urea nitrogen Potassium Creatinine Sodium Glucose Calcium Total and direct bilirubin Total protein Total cholesterol HDL-cholesterol LDL-cholesterol Triglyceride	Alanine Aminotransferase (AST) Aspartate Aminotransferase (ALT) Alkaline phosphatase (ALP) Hypothalamic-pituitary-adrenal axis evaluation: adrenocorticotropic hormone (ACTH) Cortisol Inflammatory markers: Erythrocyte sedimentation rate (ESR) C-reactive protein (CRP)

Routine urinalysis	
• Specific gravity• pH, glucose, protein, blood, ketones, bilirubin, urobilinogen, nitrite, leukocyte esterase by dipstick• Microscopic examination (if blood or protein is abnormal)
Urine culture	
• Urine culture will be performed at Screening and on Day 29 or early withdrawal
Other screening tests	
• Urine drug screen (to include at minimum: amphetamines, barbiturates, cocaine, opiates, cannabinoids and benzodiazepines)• Serum β-human chorionic gonadotropin (hCG) pregnancy test (as needed for women of childbearing potential [WOCBP]) at Screening• Urine pregnancy tests (pre-dose on Day 1, and Day 29 or early withdrawal)• Serology (HIV antibody, HBsAg, and HCV antibody)• TB blood tests• NAAT for Neisseria. gonorrhoeae and Chlamydia. trachomatis

Investigators must document their review of each laboratory safety report.

Appendix 2 Pain Score 0-10 Numerical Rating Scale

The NRS is a unidimensional measure of pain intensity in adults, including those with chronic pain due to rheumatic diseases.

The NRS is a segmented numeric version of the visual analog scale (VAS) in which a respondent selects a whole number (0–10 integers) that best reflects the intensity of his/her pain. Respondents are most commonly asked to report pain intensity “in the last 24 hours” or an average pain intensity. The common format is a horizontal bar or line. Similar to the VAS, the NRS is anchored by terms describing pain severity extremes.

The 11-point NRS ranges from ‘0’ representing 1 pain extreme (eg, “no pain”) to ‘10’ representing the other pain extreme (eg, “pain as bad as you can imagine” or “worst pain imaginable”).

Subjects will select the level that best describes their maximum and average bladder pain over the last 24 hours, and their bladder pain at the moment, respectively.

PAIN SCORE 0-10 NUMERICAL RATING										
 0	 1	 2	 3	 4	 5	 6	 7	 8	 9	 10
No pain	Moderate pain						Worst possible pain			

Appendix 3 Symptoms of Interstitial Cystitis/Bladder Pain Syndrome

Subjects will select the level that best describes the severity of other symptom from their bladder over the last 24 hours.

	Not at all	Mild	Moderate	Severe
Pain				
Burning				
Discomfort				
Pressure				

Appendix 4 Voiding Frequency

Subject will record their responses to the following items every day.

Daytime urine:

Night time urine (urination wake you up from sleeping):

Appendix 5 Frequency of Bladder Pain

Subject will select the level that the best describes frequency of bladder pain when they urinate and voiding frequency caused by bladder pain.

Never	Rarely	Sometimes	Always
			

Appendix 6 Voiding Volume

Subject will record 5 times of voiding volume with the time in a day. First voiding in the morning and before you go to bed are preferable.

	Time (24-hour notation)	Volume
	Record by container with scale Select BLQ if less than the minimum scale	
1	Time (24-hour notation)	Volume
	:	mL/ BLQ
2	Time (24-hour notation)	Volume
	:	mL/ BLQ
3	Time (24-hour notation)	Volume
	:	mL/ BLQ
4	Time (24-hour notation)	Volume
	:	mL/ BLQ
5	Time (24-hour notation)	Volume
	:	mL/ BLQ

Appendix 7 Acetaminophen Consumption

Please record the time, the number of tablets and bladder pain when you take rescue medicine.

[figure not shown]
	Time (24-hour notation)	Please fill in from getting up to getting up the next day	Number of tablets	Please fill in the number of tablets taken
	Pain score	Each time you took acetaminophen, select the level of your bladder pain from 1 – 10*		
1	Time (24-hour notation)	:	Number of tablets	
	Pain score	 0  1  2  3  4  5  6  7  8  9  10		
2	Time (24-hour notation)	:	Number of tablets	
	Pain score	 0  1  2  3  4  5  6  7  8  9  10		
3	Time (24-hour notation)	:	Number of tablets	
	Pain score	 0  1  2  3  4  5  6  7  8  9  10		
4	Time (24-hour notation)	:	Number of tablets	
	Pain score	 0  1  2  3  4  5  6  7  8  9  10		
5	Time (24-hour notation)	:	Number of tablets	
	Pain score	 0  1  2  3  4  5  6  7  8  9  10		
6	Time (24-hour notation)	:	Number of tablets	
	Pain score	 0  1  2  3  4  5  6  7  8  9  10		

* 0: No pain, 5: Moderate pain, 10: Worst possible pain

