Efficacy Assessments:	
• Subject Daily diary
○ Bladder pain (maximum and average bladder pain, bladder pain at that time)○ Symptoms of IC/BPS (pain, burning, discomfort, and pressure)○ Voiding frequency
▪ Diurnal (from the time of getting up to the time of going to bed)▪ Nocturnal (overnight)○ Frequency of bladder pain (frequency of bladder pain when subjects urinate and frequency of voiding caused by bladder pain)○ Voiding volume○ Acetaminophen consumption (amount of acetaminophen, date and time of taking medicine and bladder pain at that time)• Patient reported outcome (PRO) at the study site
○ Interstitial Cystitis Symptom Index Score/Problem Index (ICSI/PI) score○ BPIC-SS○ Global Response Assessment (GRA)• Voiding volume (during confinement)• Inflammatory markers: Erythrocyte sedimentation rate (ESR), C-reactive protein (CRP)
Statistical Methods:	
Analysis populations:
 
• The intention-to-treat (ITT) population includes all randomized subjects regardless of whether the subject received any IP or had any efficacy assessment collected.• The Per-protocol (PP) population includes all ITT subjects without major protocol deviation.• The safety population includes all randomized subjects who received IP. If a subject receives IP other than the subject's randomized treatment

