6.9.3 Rescue Medication

Acetaminophen will be provided to subjects as a rescue medication for relief of the bladder pain. Subjects will be required to use only the provided acetaminophen to treat breakthrough pain in the bladder. Acetaminophen will be used only if subjects feel the need to use rescue medication and will not be used excursively. The usage of subject's acetaminophen is 1 or 2 caplets at 1 time and the limitation is up to 3,000 mg/day. An interval between doses of at least 4 hours is recommended.

Subjects will be recommended not to use other medications that contain acetaminophen, such as cold medicine which may cause the subject to consume more than 3,000 mg of acetaminophen in 1 day.

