8.3.1.6 Acetaminophen Consumption and Pain

- Assessment Points: Daily from Day -7 until Day 29.
- Item: See [Appendix 7](#)
- Method: Subjects will record daily amount of acetaminophen (rescue medication), date and time of taking medicine over the last 24 hours (from the time of going to bed to the time of next going to bed), and bladder pain at that time when subject takes acetaminophen.

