11.5 Efficacy Analyses

All efficacy analysis will be conducted based on the ITT population.

Each efficacy assessment will be summarized for all subjects by treatment group at each assessment visit. The assessments collected on daily diary will be calculated by average at each assessment visit. Efficacy assessments from the daily diary such as bladder pain and symptoms of IC/BPS will be summarized by study day in addition to the summary at each assessment visit.

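### Pain scored when rescue is taken exists only for rescue users, so its treatment-group mean is not a fair efficacy comparison

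*Combined protocol and SAP*

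**What the plan says.** The synopsis, under Efficacy Assessments, includes in the daily diary acetaminophen consumption, made up of "amount of acetaminophen, date and time of taking medicine and bladder pain at that time". Section 8.3.1.6 repeats the item and ties the score to an intake: "bladder pain at that time when subject takes acetaminophen". The form in Appendix 7 has one pain score per intake and instructs: "Please record the time, the number of tablets and bladder pain when you take rescue medicine". It has no entry for a moment without an intake.

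Section 6.9.3 leaves the intake to the subject and sets no pain threshold: "Acetaminophen will be used only if subjects feel the need to use rescue medication".

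Section 11.5 states: "Each efficacy assessment will be summarized for all subjects by treatment group at each assessment visit". It adds: "The assessments collected on daily diary will be calculated by average at each assessment visit". No diary field is excepted. Section 11.6.3 states: "Missing data will not be imputed and will be excluded from the analysis". Nothing separates a day on which no rescue was needed from a day with missing data.

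Section 8.3.1.1 collects maximum, average and current bladder pain on a 0 to 10 scale every day from Day -7 to Day 29, whether or not rescue is taken.

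**The concern.** Whether a rescue-time score exists is itself an outcome after randomisation. If a dose works, some episodes no longer prompt rescue, and those are likely to be the milder ones. The scores that remain come from a more severe selection. A subject who stops needing rescue, which is the best result on this item, contributes no score.

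Read as written, sections 11.5 and 11.6.3 then compare group means taken over different kinds of episode in different subjects. Randomisation does not protect that comparison. The resulting table would sit beside the other preliminary-efficacy tables, with six subjects per dose, and could make a real benefit look small, absent or, in some circumstances, reversed.

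**Working it through.** **Design figures.** Four cohorts at 6:2 give 4 × 6 = 24 on SI-722 and 4 × 2 = 8 on placebo, total 32, matching section 3.4. Placebo is pooled (section 11.6), so each dose is compared 6 against 8. The documents give no figure for pain at rescue; every pain level, SD and threshold below is an assumption.

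**Attenuation.** Let episode pain be normal with mean μ and SD σ, with rescue taken at pain T or above. The mean recorded score is

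E[X | X ≥ T] = μ + σ φ(a) / (1 − Φ(a)), where a = (T − μ)/σ.

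Example with σ = 2, T = 6 and a true fall from 6 to 4:
- Untreated: a = 0, so 6 + 2 × 0.3989/0.5 = 7.60.
- Treated: a = 1, so 4 + 2 × 0.2420/0.1587 = 7.05.
- Visible fall: 0.55 of 2 points (27%). The share of moments with rescue drops from 50% to 16%.

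Visible fall across the assumed range (untreated mean 6):

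| T | σ | true fall 1.5 | true fall 2 |
|---|---|---|---|
| 5 | 1.5 | 0.61 (41%) | 0.74 (37%) |
| 5 | 2.0 | 0.59 (39%) | 0.74 (37%) |
| 5 | 2.5 | 0.58 (39%) | 0.73 (37%) |
| 6 | 1.5 | 0.41 (27%) | 0.50 (25%) |
| 6 | 2.0 | 0.44 (29%) | 0.55 (27%) |
| 6 | 2.5 | 0.46 (30%) | 0.58 (29%) |

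The mean shows 0.41 to 0.74 points, or 25% to 41% of the true fall. Widening the range to T = 5 to 7 and true falls of 1 to 3 points gives 15% to 44%.

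**Reversal through episodes.** Rescue episodes at 4, 5, 6, 7 and 8 average 30/5 = 6.0. If those at 6 or below disappear and the others do not change, 7 and 8 remain, with mean 7.5. The measure worsens by 1.5 points while episodes fall from 5 to 2 (60%).

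**Reversal through subjects.** Half the subjects have pain 5 and half have 8, with rescue at 5 or above. The mean at rescue is 6.5. If everyone improves by 1 point, true mean pain falls from 6.5 to 5.5. The milder half, now at 4, stop rescue, and the mean at rescue rises to 7.0. If everyone improves by 2 points, it falls to 6.0. Reversal is possible but not general.

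**At trial size.** Simulated trials of 6 against 8 used a true 2-point fall, mean pain 6, between-subject SD 1.5, within-subject SD 1, and a rescue threshold with mean 6 and SD 0, 1 or 2. The dose group's mean pain at rescue was at or above placebo in 6% to 12% of trials, against under 1% for mean pain over all moments.

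**Measures defined for everyone.** In the same model in large samples, with threshold SD 1, a true 2-point fall moves:
- mean pain over all moments from 5.99 to 4.00;
- subjects using rescue from 86% to 50%;
- intakes per day, counting zero for non-use, from 2.00 to 0.67;
- mean pain at rescue only from 7.15 to 6.38.

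**The case against.** Section 11.5 never names pain at rescue. Its named diary examples are bladder pain and IC/BPS symptoms. The score shares a parenthesis with date and time of intake, which nobody would average by group, so the general rule cannot apply literally to every field there. Section 11 also leaves data handling to the SAP, and the combined document has no SAP text that settles the matter. This stands as a limit: the averaging follows from a general rule and is not an explicit instruction. But no text takes the field out, and following the rule as written produces the conditional mean.

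The item is also small. It is one sub-field under a secondary objective, the reporting is descriptive, no efficacy test is named, and tablet amount and three daily pain scores are collected alongside it. A reader might infer that the trial's efficacy assessment as a whole is compromised. The documents do not support that, because the section 8.3.1.1 scores do not depend on rescue.

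A reader might also infer that an effective dose will look worse on this measure. A uniform benefit with one common threshold shrinks the difference without reversing it. Reversal needs milder episodes or subjects to leave first, or chance in small groups.

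Finally, a reader might want to rescue the data by folding rescue-time scores into the daily maximum or the bedtime current score. That would carry the selection into measures now free of it, since only rescue days gain readings and a maximum can only rise. With independent reporting error of SD 1 in two readings of the same true maximum, a rescue day rises by 1/√π ≈ 0.56 points. If rescue days fall from 50% to 16%, the arm using less rescue gains 0.56 × 0.34 ≈ 0.19 points with no change in true maximum pain. The bedtime maximum already covers the preceding 24 hours.

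**Conclusion.** The point holds for this one field. As sections 11.5 and 11.6.3 are written, mean pain at rescue by treatment group is conditional on a post-randomisation choice and cannot be read as a treatment effect. Under the assumed normal model it shows roughly a quarter to two fifths of a true fall of 1.5 to 2 points, and under less regular patterns it can point the wrong way. The sizes depend on assumed pain levels, SDs and thresholds; the selection itself follows from how the score is collected. The primary objectives and the daily pain scores are untouched. It is worth correcting because the correction is cheap and the table would otherwise invite misreading.

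**What to change.** - In section 11.5 and the SAP, exclude pain at time of rescue from the treatment-group efficacy means. Give it in listings, or describe it among rescue users with the numbers of users and intakes, labelled as not a treatment comparison.
- Compare rescue by tablets per day and number of rescue-free days over all ITT subjects with diary data. Count a completed diary day without rescue as zero; only a day without a completed diary is missing under section 11.6.3.
- Leave the daily maximum and bedtime current pain scores as collected, without merging in rescue-time scores.
- Before deriving per-day rescue use, reconcile the recording day: section 8.3.1.6 runs from bedtime to bedtime, Appendix 7 from getting up to getting up.

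The cost is one fewer efficacy table, some SAP wording and a little more programming. No new data or visits are needed.
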